12.3.5 Subgroup Analyses

Subgroup analyses will be performed based on gender and region (USA and Russia).

12.4 Sample Size

The power of this study to establish that the true infection rate is less than 1 per subject per year depends primarily on the unknown true infection rate. However, on the assumption that the number of serious bacterial infections (SBIs) per year follows a negative binomial distribution with mean μ and variance $\sigma^2 = \mu(1+\phi\mu)$ where μ is the population mean infection rate per year and ϕ is an overdispersion parameter reflecting possible variability in individual subject-specific rates, an estimate of the power can be made for a range of assumptions about the true infection rate.

The following table shows the estimated power of a study with 40 subjects (Cohort 1) or 20 subjects (Cohort 2) to achieve an upper 99% confidence limit below 1, for various true values of the population mean infection rate assuming a range of overdispersion from $\phi=0$ (corresponding to a Poisson distribution with no overdispersion) to $\phi=2.0$. These results were obtained using standard one-sample power calculations for testing the one-sided null hypothesis, $H_0: \mu \geq 1$, against the alternative hypothesis, $H_1: \mu < 1$, where μ is the population mean number of SBI's per subject per year. Specifically, the estimated power is given by $\text{Power} = 1 - \beta = \Pr[m + Z_{1-\alpha}\sigma < 1 | H_1]$ where m is the sample mean rate of infection, $Z_{1-\alpha} = 2.326$ is the standard normal quantile for an upper 99% confidence limit,

and $\sigma^2 = \mu(1+\phi\mu)$ is the true variance under the alternative hypothesis H_1 for some specified value μ that is less than 1.

Table 5. Calculations on Statistical Power

True population infection rate per subject per year and possible overdispersion		Chance of upper 99% one-sided confidence limit being below 1	
SBI rate μ	Overdispersion parameter ϕ	N=40 (Cohort 1)	N=20 (Cohort 2)
0.40	0 (Poisson)	99.9%	97.2%
	2.0	98.4%	79.8%
0.45	0 (Poisson)	99.8%	91.0%
	2.0	92.4%	63.1%
0.50	0 (Poisson)	98.4%	79.8%
	2.0	79.8%	46.4%
0.55	0 (Poisson)	93.5%	65.1%
	2.0	62.6%	32.5%
0.60	0 (Poisson)	82.6%	49.3%
	2.0	45.0%	22.1%

The study therefore has adequate power (80% or greater when rounded) provided that the true rate of serious bacterial infections in the study population is 0.50 per subject per year or below for adults, or 0.40 per subject per year or below for children, and if the assumption of a negative binomial distribution (or Poisson distribution when $\phi=0$) is appropriate.

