- The volume of distribution at steady-state (V_{ss})
- Mean residence time (MRT)
- Total body clearance (CL)
- Terminal half-life ($t_{1/2}$)

Statistical Methods:

Sample size

To calculate the approximate power for this study, it is assumed that the number of SBIs experienced per subject per year follows a negative binomial distribution with mean μ and variance $\sigma^2 = \mu(1+\phi\mu)$ where ϕ represents an overdispersion parameter reflecting possible inter-subject variability in the rates of SBIs between subjects. To demonstrate efficacy, it is required that the observed mean number of SBIs across the study population should have an upper 99% one-sided confidence limit below 1 infection per subject per year. This is equivalent to testing the one-sided null hypothesis, $H_0: \mu \geq 1$, against the alternative hypothesis, $H_0: \mu < 1$, where μ is the population mean rate of SBI's per subject per year.

Based on the mean and variance of the negative binomial distribution, standard one-sample power calculations for comparison of an observed mean with a theoretical alternative hypothesis indicate that for a study with 40 subjects (Cohort 1), the probability of the upper one-sided 99% confidence limit being less than 1 remains above 80% ($power \geq 0.798$) for overdispersion ranging from $\phi=0$ (corresponding to a Poisson distribution with no overdispersion) to $\phi=2$ provided that the true mean number of SBIs per subject per year in the population lies below 0.50. For a sample of 20 subjects (Cohort 2), this probability remains at or above 80% ($power \geq 0.798$) for overdispersion ranging from $\phi=0$ to $\phi=2$ provided that the true mean

number of SBIs per subject per year in the population lies below 0.40 (or 0.50 in the case when there is no overdispersion).

For practical purposes, the study should be considered adequately powered to demonstrate efficacy for a population in which the true incidence of serious acute bacterial infections is below 0.50 per subject per year.

General statistical approach

Analyses will be presented for the adult cohort (Cohort 1) and the pediatric cohort (Cohort 2) regardless of Study Group both separately and combined.

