4.1 Main Study

Cohort 1 will enroll approximately 50 subjects aged 17 to 80 years to achieve at least 40 evaluable subjects.

Cohort 2 (children) will enroll approximately 25 subjects to achieve at least 20 evaluable subjects. Cohort 2 will enroll up to 6 subjects aged 2 to <6 years, at least 6 subjects 6 to <12 years, and at least 6 subjects aged 12 to <17 years.

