12.1 Analysis Populations

The safety analysis set will consist of all subjects who are enrolled into the study and received study product. The all treated population analysis set will be the same as the safety set. A modified per-protocol population analysis set will be defined as all subjects in the full all treated population set who remain in the study for at least 6 infusions.

A per-protocol (PP) analysis set will consist of all subjects in the all treated population set who complete the whole 12-month study period and who do not have any major protocol violations as described in the Data Handling Plan.

The analyses described below will be presented for all subjects in the all treated population, the modified PP population, and the PP population as follows:

- Cohort 1 only;
- Cohort 2 only;
- Each of the 3 age groups within Cohort 2;
- Cohorts 1 and 2 pooled.

The primary efficacy analysis will be based on the all treated population analysis set, with separate analyses for Cohort 1 and Cohort 2.

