12.2 Handling of Missing Data

For the primary efficacy analysis, the method of maximum likelihood estimation will be used in conjunction with a negative binomial model to obtain a 99% one-sided upper confidence limit on the rate of serious bacterial infections. Since the resulting confidence interval leads to valid statistical inference assuming missing data are missing at random, no data imputation will be used in this analysis. With respect to safety and secondary endpoints, no data imputation will be used in the analysis of any other data from this study including the PK evaluations. Missing data will be omitted from summary statistics.

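### The stated 80% power belongs to a known-variance, rate-scale limit, not the planned regression limit, which at phi = 2 gives 40% to 64% at N = 40/20

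*Protocol*

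**What the plan says.** **Power.** Protocol 12.4 describes its Table 5 as follows: "These results were obtained using standard one-sample power calculations for testing the one-sided null hypothesis" that the rate is at least 1. The formula shown adds 2.326 times the true standard deviation to the sample mean. SAP section 4 repeats the text and the table. Table 5 uses N = 40 and N = 20 and prints 79.8% at phi = 2 for both boundary cases: adults at 0.50 and children at 0.40.

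**Claim.** Protocol 12.4 concludes: "The study therefore has adequate power (80% or greater when rounded) provided that the true rate of serious bacterial infections" does not exceed 0.50 (adults) or 0.40 (children). For 40 adults with a true rate below 0.50, the synopsis says that "the probability of the upper one-sided 99% confidence limit being less than 1 remains above 80" per cent across phi from 0 to 2, with a minimum of 0.798 in brackets. For 20 children it makes the same claim below 0.40, or 0.50 without overdispersion. It then says: "For practical purposes, the study should be considered adequately powered to demonstrate efficacy for a population in which the true incidence" is below 0.50, without separating the cohorts.

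**Analysis.** Protocol 12.2 says "the method of maximum likelihood estimation will be used in conjunction with a negative binomial model". Protocol 12.3.2 and SAP 10.1 add time on study as an offset. The sample code in SAP 10.1 instead fits a log-link Poisson model with deviance scaling (DSCALE) and alpha 0.02. Neither document says which kind of negative binomial interval is meant.

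**Numbers analysed.** Protocol 12.1: "The primary efficacy analysis will be based on the all treated population analysis set, with separate analyses for Cohort 1 and Cohort 2". Protocol 4.1 says of the adults: "Cohort 1 will enroll approximately 50 subjects aged 17 to 80 years to achieve at least 40 evaluable subjects". By the same section, the pediatric cohort "will enroll approximately 25 subjects to achieve at least 20 evaluable subjects".

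**The concern.** Power has to refer to the limit that decides success. The tables use a limit that is symmetric around the observed rate, with a variance nobody has to estimate. The planned limits come from a log-link model with estimated dispersion. They stretch upward, towards the threshold of 1, so they are harder to pass.

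The 0.50 and 0.40 thresholds are the documents' only quantitative support for 40 and 20 evaluable subjects, and each cohort has its own primary analysis. If a cohort, above all the pediatric one, missed the limit, readers would judge that result against a claimed 80% power which the analysis did not have.

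**Working it through.** **Inputs.** One-sided 99% limit, z = 2.326, success if the limit is below 1, variance mu(1 + phi·mu), phi from 0 to 2, N = 40 and 20 (Protocol 12.4); about 50 and 25 enrolled (Protocol 4.1); about one year on IMP (Protocol 3.5.1). Full one-year exposure for everyone is an assumption unless stated otherwise.

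**Step 1: reproduce the printed figures.** Power = Phi[(1 − mu)·√N / √(mu(1 + phi·mu)) − 2.326].

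- Adults, 0.50, phi 2, N = 40: 0.50 × 6.325 / 1.000 = 3.162; 3.162 − 2.326 = 0.836; power 79.85%.
- Children, 0.40, phi 2, N = 20: 0.60 × 4.472 / 0.8485 = 3.162; power 79.85%.

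All 20 cells reproduce, apart from one rounding (99.99% printed as 99.9%). The printed formula omits the division by √N; taken literally it gives 3.4% in the adult cell.

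**Step 2: the limits the plan points to.** With m the observed mean over one-year exposures:

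- Negative binomial, Wald on the log scale: m·exp{2.326·√[(1/m + phi-hat)/N]}, phi-hat by maximum likelihood, not below 0.
- SAP code: m·exp{2.326·√[s/(N·m)]}, s = Poisson deviance/(N − 1).

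**Step 3: why power falls.** At 0.50, phi 2, N = 40, the threshold lies 3.16 standard errors away on the rate scale. On the log scale it is −ln(0.50)/√[(2 + 2)/40] = 0.693/0.316 = 2.19. For children at 0.40, N = 20, it is 0.916/√[(2.5 + 2)/20] = 0.916/0.474 = 1.93. The closed form Phi[−ln(mu)/√((1/mu + phi)/N) − 2.326] then gives 44.7% and 34.7%, and 55.0% and 43.4% at N = 50 and 25.

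**Step 4: simulation.** Gamma-Poisson counts, 100,000 trials per cell. Power as negative binomial Wald / SAP code:

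| Cohort, rate | N | phi 0 | phi 1 | phi 2 | Printed, phi 0 and 2 |
|---|---|---|---|---|---|
| Adults, 0.50 | 40 | 85% / 85% | 63% / 71% | 48% / 64% | 98.4%, 79.8% |
| Adults, 0.50 | 50 | 93% / 93% | 75% / 82% | 59% / 74% | not given |
| Children, 0.40 | 20 | 63% / 71% | 48% / 61% | 40% / 56% | 97.2%, 79.8% |
| Children, 0.40 | 25 | 80% / 81% | 62% / 71% | 49% / 65% | not given |

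Trials with no SBI, for which the log-link models have no finite limit, count as failures. They are at most 0.3% of trials in these cells. For children at 0.50 without overdispersion, N = 20, the power is 40% / 47% against a printed 79.8% (20,000 trials).

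If the extra 10 adults or 5 children leave at a uniform time during the year (assumption; 6,000 trials), phi 2 gives 54% / 72% and 44% / 64%, and phi 0 gives 90% / 91% and 70% / 80%.

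**Step 5: other negative binomial intervals at phi 2, and one-sided size at a true rate of 1.**

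| Limit | Power, adults 0.50, N = 40, 50 | Power, children 0.40, N = 20, 25 | Size, N = 40, 20 (nominal 1%) |
|---|---|---|---|
| Rate scale, estimated phi | 73%, 80% | 72%, 77% | 5.4%, 8.5% |
| Log-scale Wald | 48%, 59% | 40%, 49% | 1.9%, 2.8% |
| Profile likelihood | 36%, 48% | 20%, 29% | 1.2%, 1.5% |
| SAP code (Poisson, DSCALE) | 64%, 74% | 56%, 65% | 3.3%, 4.2% |

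The only entry at 80% (rate scale, N = 50) has size 4.9%.

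**Step 6: true rates that give about 80% power, at phi 0 and phi 2 (20,000 trials).**

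- Adults, Wald: 0.52 and 0.36 (N = 40); 0.57 and 0.41 (N = 50). SAP code: 0.52 and 0.43; 0.56 and 0.47.
- Children, SAP code: 0.36 and 0.28 (N = 20); 0.40 and 0.33 (N = 25).
- Children, Wald: at phi 0, 0.32 (N = 20) and 0.40 (N = 25). At phi 2, 0.18 and 0.24, but only if a trial with no SBI counts as a success. Counted as failures, they hold power at N = 20 to 76%, 78% and 73% at rates 0.10, 0.15 and 0.20.

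**The case against.** The tables contain no arithmetic error. The method is disclosed, and the synopsis calls the power approximate. The interval type is not named, so the Wald figures depend on a choice the documents do not make. The only concrete specification, the SAP code, is less adverse. Phi = 2 is the edge of the sponsor's range, and 0.50 and 0.40 are the highest rates claimed. With 50 adults and full exposure, the adult statement holds at phi 0 (93% under both limits) and phi 0.5 (85% / 87%), and at phi 1 under the SAP code (82%). No expected SBI rate is stated, so nothing shows that the trial is truly underpowered: with 40 adults at 0.30 and phi 2, power is 90% / 98%.

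Most of this stands and narrows the point to a mismatch between power method and analysis method. It does not rescue the claim. The synopsis covers the whole range of phi from 0 to 2, and at its edge neither log-link limit reaches 80% at either N. At N = 20 the pediatric claim fails at every phi examined. The unnamed interval is part of the defect, and the one alternative that reaches 80% does so with a size well above 1%.

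**Conclusion.** The concern holds. The tables are right for their own formula, but that formula is not the planned analysis, and the error is in the optimistic direction. At phi = 2 the printed 79.8% overstates power by about 32 points (Wald, 48%) or 16 points (SAP code, 64%) for adults at N = 40. For children at N = 20 it overstates by about 40 or 24 points (40% and 56%). Analysing about 50 and 25 subjects narrows the gap without closing it.

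The adult claim at 0.50 holds at phi 0. The pediatric claim at 0.40 holds at phi 0 only with about 25 fully exposed children. These figures assume gamma-Poisson counts and, except where noted, one year on IMP per subject. They concern the stated power and thresholds. They do not show that the trial would fail at a lower true rate.

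**What to change.** 1. Reconcile the Poisson DSCALE code in SAP 10.1 with the negative binomial text, and name the interval type.
2. State the rule for a cohort with no SBIs.
3. Recompute Protocol Table 5 and SAP Table 1 by simulating the reconciled analysis at N = 40/20 and 50/25, with the exposure assumption stated and the size at a true rate of 1 shown. Replace the printed formula, which lacks the division by √N.
4. Replace the 0.50 and 0.40 adequacy statement with the simulated thresholds by phi.
5. Limit the synopsis sentence on 0.50 to Cohort 1, as far as the new table supports it. Table 5 itself gives Cohort 2 only 46.4% at 0.50 and phi 2.

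The cost is a short simulation and restated figures in both documents. The sample size and success criterion stay as they are; the drawback is a less favourable stated power.

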12.5 Interim Analysis

Two interim safety analyses will be performed to allow the DSMB and FDA to evaluate safety data from the first 15 subjects (Section 3.1) before Group 3 begin receiving the IMP.

No other interim analysis is planned. However, when all subjects in Cohort 1 have completed the LTSV, and all data have been fully reconciled, a database lock of Cohort 1 will occur, and a Clinical Study Report will be prepared in support of a BLA for the adult population. All available safety data relating to Cohort 2, available at the time of the Cohort 1 database lock, will be included in this report. When all subjects in Cohort 2 have completed the LTSV, this process will be repeated, and a separate Clinical Study Report will be prepared in support of a BLA for the pediatric population. This second report will also include the pooled analysis of the two cohorts.

13 Management of Investigational Medicinal Product

Detailed instructions are specified in the IMP Manual at each site.

13.1 Packaging and Labeling

The IMP, ProMetic BioTherapeutics Immune Globulin Intravenous Solution 10%, is a sterile, 10% liquid preparation of highly purified immune globulin (IgG) derived from pools of human plasma of at least 1000 donors (21 CFR, §640.102) for IV administration under aseptic conditions.

The IMP is filled in 50 mL (5 g) single-use, type-1 glass bottles sealed with a rubber stopper and an aluminum seal with plastic flip-top cap.

Vial labels will include information to comply with US regulations:

- “Caution: New Drug - Limited by Federal (or United States) Law to Investigational Use Only”
- The protocol number “2004C009G”
- The product volume (50 mL) and 10% concentration
- The lot number
- The recommended storage conditions
- The name of the Sponsor
- Expiry date will not be included, as stability testing will be ongoing. Therefore, the documentation of the applicable expiry dates will be provided according to the lot number and stored in the IMP files at the site with the Investigator and/or Research Pharmacist, if applicable.
- Labeling for the shelf cartons will also bear this information.

Vial labels for non-US sites will include information to comply with local regulations.

13.2 Storage

The IMP must be stored refrigerated at 2-8°C in a secured area until used. The temperature in the storage area should be monitored with properly calibrated instruments and monitored on a temperature log.

13.3 Accountability

The PI or designee is responsible for maintaining accurate inventory records of IMP. The PI or designee will inventory all IMP shipments upon receipt, acknowledge possession by signing and returning all required documentation to the Sponsor or CRO. The PI must

ensure that all drug supplies are kept in a secure location at the site in accordance with recommended storage conditions. Inventory records for the IMP will include:

- Protocol name, number, and sponsor.
- Product name and description.
- Study site and PI name.
- Product lot number and Expiry Date(s)/Re-test date.
- Number of vials, sizes received from the Central Drug Repository.
- Number of vials dispensed, date and time of dispensing and study subject for whom product was dispensed.
- Product balance.
- Name and title of qualified individual dispensing product.

These records will be reviewed by the Monitor, and may be reviewed by regulatory agencies.

All correspondence with the sponsor regarding the stability and product release should be kept with the study specific documents at site and/or the pharmacy as applicable.

13.4 Shipment, Returns, and Destruction

The IMP will be shipped from ProMetic BioTherapeutics to a selected Central Drug Repository and from the Central Drug Repository to the sites at a temperature of 2-8°C. During shipment, the temperature of the drug will be monitored to ensure the required temperature conditions are maintained. The PI or designee will be responsible for checking the number of vials and the condition of the vials received and entering this information into the drug accountability records, reporting the condition to ProMetic BioTherapeutics, the CRO and/ or the Central Drug Repository and return the data logger and all required documentation to the Central Drug Repository. At the end of the study, or upon request by the sponsor, all unused, partially used or empty vials will be returned to the sponsor or the Central Drug Repository or destroyed at the site after accountability has been completed by the Monitor.

13.5 Preparation

The IMP should be inspected for particulate matter and discoloration prior to administration. The solution should be clear or slightly opalescent. Solutions that are cloudy or have particulates **must not be used. Vials must not be shaken.**

The IMP can be infused directly from the vials or the IMP may be pooled and aseptically transferred into an empty sterile IV bag before administration as follows:

- The protective caps from the product vials must be removed.
- The exposed central portion of the rubber stopper must be wiped with an isopropyl alcohol swab.
- The dose will be calculated based on the prescription provided by the PI which will be based on the subjects' weight and trough levels and calculated in a mg/kg dose.
- IMP preparation will be made allowing for rounding up to the next 10mL.
- IMP preparation can also be rounded down to the previous 10mL as long as the dose remains in the range mandated by the protocol (200mg-800mg/kg)
- If the site pools the IMP into an infusion bag, then an appropriate volume of IMP will be drawn into a syringe, aseptically transferred into an appropriately sized sterile IV bag and labeled. The rounded dose will be pooled into the bag together with a predetermined extra volume per site for priming the tube, if applicable. Saline, DW5 or IMP can be used to flush the tubing, per standard of care.
- Flushing or priming the IV set with the IMP will be allowed, per the usual practices of the site. Any IMP used for this purpose will be included as part of the IMP dose.
- Any other approved fluid (Saline, DW5) used to flush or prime IV tubing must be documented in the eCRF and not included as the IMP dose volume.
- All vials empty and partial will be saved.

Pooled infusions must be prepared by a pharmacist or appropriately qualified designee.

In the event that a pharmacy will not be used, the IMP may be stored in an alternate location (e.g., a refrigerator monitored by site staff, etc.), as long as such location meets the requirements given in Section 13.2. In this case, the IMP should only be pooled if the aseptic technique described above can be ensured, and the person performing this task is appropriately qualified and working under the supervision of the Investigator.

Empty and partially used study drug vials must be maintained for drug accountability. These supplies should be clearly marked by subject (e.g., empty and partially empty vials from a single infusion should be placed in a plastic bag that bears the subject number and initials and date) and must not be discarded until authorization has been provided by the CRA. The volume left behind in partially empty vials will be recorded as

- <25%
- 25%-50%
- 50%-75%
- 75%-100%

For any single infusion to a subject, the same lot must be used; no mixing of lots. However, over the 13 or 17 infusions for a subject, different lots can be used. Prior to infusion, the IMP should be brought to room temperature or body temperature, and once this process has occurred, unused IMP should not be returned to the refrigerator for future use.

13.6 Dose and Administration of IMP

Note: The dose and administration of CP for subjects on the Waiting Period will be per standard care, as determined by the Investigator in consultation with the treating physician. This section only applies to IMP.

13.6.1 IMP Dose

The IMP dose should be consistent with previous IGIV or IGSC treatment.

When subjects receiving IGIV enter the study, the IMP will be administered initially at a dose and schedule based on the subject's previous IGIV dosing schedule (3- or 4-week interval). Subjects on a 21-day cycle when they enter the study will remain on a 21-day cycle, and subjects on a 28-day cycle will remain on a 28-day cycle. The study dose will be calculated by the Investigator using the subject's body weight (200-800 mg/kg, allowing for $\leq 25\%$ change).

Subjects who are on IGSC when they enter the study must have previously tolerated IGIV use at either a 21-day or a 28-day cycle, and these subjects will be switched from IGSC to IGIV treatment at the same cycle as their previous IGIV treatment. However, because doses are adjusted in an ongoing manner for multiple reasons, including weight changes, the initial study dose may not be the same as the previous IGIV dose. Instead, the study IGIV dose may be based on the current IGSC dose and will be calculated by multiplying the weekly IGSC dose by 3 (for a 21-day cycle) or by 4 (for a 28-day cycle) and then dividing by the dose-adjustment coefficient as indicated by package insert.

The PI may change the dose and/or dosing interval in order to maintain a trough level of ≥ 5 mg/mL. For example, such changes may be necessary because of assessments of AEs or other safety assessments, or changes in the subject's weight. If at any visit after the first infusion of IMP, a subject's body weight has changed by 5% or more from the baseline value, the IMP dose will be adjusted accordingly. Any changes in the dose and/or dosing interval must be recorded on the subject's CRF, along with the reason for the change.

